- f **Vital Signs:** Blood pressure, heart rate, temperature, and respiration rate required at Screening, to be taken just before starting infusion, every hour during the infusion, and at the end of infusion on D1, D8, D15 and D22 of Cycle 1; and to be taken just before starting infusion at D1 and D15 of each subsequent cycle and as clinically indicated, at the EOT visit, and at post treatment follow up visits at 60 and 90 days after last treatment.
- g **12-Lead ECG:** To be performed at Screening and then as clinically indicated.
- h **Chest X-ray:** To be performed at Screening and then as clinically indicated.
- i **Pregnancy Test:** Women of child bearing potential must have a negative serum pregnancy test result within 7 days prior to first IMP administration. During the study, test to be done on Day 1 of each cycle prior to the study treatment, at the end of treatment, and then every month for 5 months following the last dose of Isatuximab or 6 months following the last dose of cemiplimab, whichever comes last (urine pregnancy test can be performed at home after study treatment discontinuation).

- j* **Blood Chemistry:** To be done at Screening, then prior to pre-medication and IMP administration on D1, D8, D15 and D22 of Cycle 1 and on D1 and D15 of every subsequent cycle, at the EOT visit, 60 and 90 days after last treatment and as clinically indicated. Blood chemistry includes: SGOT (AST), SGPT (ALT), bilirubin (total and direct), alkaline phosphatase, lactate dehydrogenase (LDH), sodium, potassium, chloride, bicarbonate/carbon dioxide, calcium, corrected serum calcium, magnesium, phosphate, uric acid, urea or blood urea nitrogen (BUN), serum creatinine, eGFR(MDRD formula), glucose (fasting), albumin and total protein. Thyroid stimulating hormone (TSH) will be assessed every second cycle, and free T4 if TSH is outside of the normal range.
- k* **Hematology:** To be done at Screening, then prior to pre-medication and IMP administration on D1, D8, D15 and D22 of Cycle 1 and D1 and D15 of every subsequent cycle, at the EOT visit, 60 and 90 days after last treatment and as clinically indicated. Hematology includes: Hemoglobin, hematocrit, RBC, WBC with differential, and platelet counts. If Grade 4 neutropenia, assess ANC every 2-3 days until $ANC \geq 0.5 \times 10^9/L$ and at least weekly thereafter until $ANC \geq 1.0 \times 10^9/L$. Blood group card to be obtained before study entry.

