Patients who discontinue study treatment due to PD: follow-up visit will be done every 3 months from the date of last study treatment administration until death or final study cut-off date. Every effort will be made to follow all patients. If survival follow-up is missed and is not obtained at the time of the scheduled interval, it should be retrieved immediately. For subsequent survival follow-up, the patient FU visit should be scheduled at the original scheduled survival follow-up interval. If the patient is unable to visit the clinical center, the follow-up may be done via phone from the Investigator or designee to the patient or the patient's caregiver or a family member, but this should be exception and any effort should be done to schedule follow-up visit at clinical center.
Patients who discontinue the study treatment without PD: will be followed every month for disease assessment until confirmation of PD or start treatment with another anti-cancer therapy whichever comes first. After PD patient will be followed every 3 months as described just above.
- kk* Includes HBsAg, anti-HBsAb, and anti-HBcAb (total and IgM) and HBV DNA in case of positive anti-HBsAg (see [Section 6.5.7](#)). Once at any time if HBV status unknown before treatment started and to be repeated if clinically indicated for patient still on treatment at the time of amended protocol 05.

Abbreviations: ADA=anti-drug antibodies; AE=adverse event; ALT=alanine aminotransferase; ANC=absolute neutrophil count; ALP=alkaline phosphatase; AST=aspartate aminotransferase; BUN=blood urea nitrogen; C=Cycle; CR=complete remission; CRF=case report form; D=Day; ECG=electrocardiogram; ECOG=Eastern Cooperative Oncology Group; EOT=end-of-treatment visit; FUP=follow-up visit; HBcAb=hepatitis B core antibody; HBsAb=hepatitis B surface antibody; HBsAg=hepatitis B surface antigen; HBV=hepatitis B virus; IgM=immunoglobulin M; IMP=investigational medicinal product; INR=international normalized ratio; LDH=lactate dehydrogenase; MDRD=Modification of Diet in Renal Disease Study; PD=pharmacodynamic or progressive disease; PK=pharmacokinetic; PR=partial remission; PS=performance status; PT=prothrombin time; aPTT=activated partial thromboplastin time; SAE=serious adverse event; sFLC=serum free light chain, SGOT=serum glutamate-oxalate transferase; SGPT=serum glutamate-pyruvate transferase; WBC=white blood cell.

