6.5.7 Guidance in case of hepatitis B reactivation occurring under study treatment

Patient still on treatment at the time of amended protocol 05 will be tested for HBV serology and HBV viral DNA once at any time if HBV status was unknown before treatment started; test will be repeated if clinically indicated.

In case of viral reactivation during study treatment (greater than 1 log₁₀ IU/mL increase in HBV DNA or reappearance of hepatitis B surface antigen (HBsAg) or detection of HBV DNA in patients with resolved infection) study treatment will be held and specialist consulted for initiation of anti-viral treatment and monitoring of the patient. Resolved infection means previous known history of acute or chronic hepatitis B or the presence of total anti-hepatitis B core antibody (HBcAb) with/without anti-hepatitis B surface antibody (HBsAb); HBsAg negative; undetectable serum HBV DNA; and normal ALT levels. Restart of study treatment should be agreed between the Sponsor, the Investigator and specialist (hepatologist) if infection is controlled. ALT and AST will be closely monitored every month up to study treatment discontinuation. HBV DNA to be done as per specialist advice.

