7.3 EXCLUSION CRITERIA

Patients who have met all the above inclusion criteria listed in [Section 7.2](#) will be screened for the following exclusion criteria:

- E 01. Has any concurrent hematology malignancy other than multiple myeloma, including:
- Active primary AL amyloidosis,
 - Concomitant plasma cell leukemia.
- E 02. Has prior exposure to:
- Isatuximab or participated clinical studies with isatuximab,
 - Any agent (approved or investigational) that blocks the PD-1/PD-L1 pathway.
- E 03. Diagnosed or treated for another malignancy within 3 years prior to the study treatment with the exception of resected/ablated basal or squamous cell carcinoma of the skin, or carcinoma in situ of the cervix, or other local tumors considered cured by local treatment, or low risk prostate cancer after curative therapy;
- E 04. Evidence of other immune related disease /conditions, including:
- Ongoing or recent (within 2 years) evidence of significant autoimmune disease that required systemic immunosuppressive treatment (ie, with use of disease modifying agents, corticosteroids or immunosuppressive drugs.). Replacement therapy (eg, thyroxine, insulin, or physiologic corticosteroid replacement therapy for adrenal or pituitary insufficiency, etc) is not considered a form of systemic treatment,
 - History of moderate immune-mediated acute drug reactions (eg, colitis, hepatitis, etc).
- E 05. History of non-infectious pneumonitis requiring steroids or current pneumonitis; history of the thoracic radiation.
- E 06. Has received a live-virus vaccination within 30 days of planned treatment start. Seasonal flu vaccines that do not contain live virus are permitted.
- E 07. Known to be HIV+, HBV+ or hepatitis A, B, or C active Infection, or active tuberculosis, or severe and active infection requiring systemic antibiotics, antivirals or antifungals within 2 weeks prior to first dose (except when used for chronic prophylaxis).
- E 08. Has allogenic HSC transplant.
- E 09. Has prior exposure to treatment, including:
- Prior treatment with idelalisib (an PI3K inhibitor)
 - Any anti-myeloma drug treatment including dexamethasone within 14 days before study entry (90 days if prior anti-CD38 treatment),
 - Patients who received anti-CD38 mAb within 6 months before study entry and had disease progression while on treatment or within 60 days after the last treatment will be excluded except the anti-CD38 refractory cohort.

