12 STUDY PROCEDURES

12.1 VISIT SCHEDULE

During the course of the study, all patients entering the study must be evaluated according to the schedule outlined in the flow charts in [Section 1.1](#), [Section 1.2](#) and [Section 1.3](#) and described below. The results of the evaluation will be recorded in the e-CRF pages until the patient is not followed anymore.

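### Flow-chart note kk and Section 6.5.7 give different rules for HBV DNA testing in on-treatment patients of unknown HBV status, and note kk's trigger is an undefined term

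*Protocol*

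**What the plan says.** Protocol Section 6.5.7 applies to patients on treatment at amended protocol 05. It states that each "will be tested for HBV serology and HBV viral DNA once at any time if HBV status was unknown before treatment started", with a repeat where there is a clinical reason.

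Note kk to the flow chart in Section 1.1 covers the same patients and the same occasion and points to Section 6.5.7. Its content differs: "Includes HBsAg, anti-HBsAb, and anti-HBcAb (total and IgM) and HBV DNA in case of positive anti-HBsAg". The flow-chart abbreviations give "HBsAb=hepatitis B surface antibody; HBsAg=hepatitis B surface antigen". Neither that list nor Section 3 has an entry for anti-HBsAg.

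Section 6.5.7 then uses the DNA result twice. Besides a known history of hepatitis B, the findings it accepts as resolved infection are "the presence of total anti-hepatitis B core antibody (HBcAb) with/without anti-hepatitis B surface antibody (HBsAb); HBsAg negative; undetectable serum HBV DNA", together with normal ALT. Treatment is held for reactivation on any of three criteria: "IU/mL increase in HBV DNA or reappearance of hepatitis B surface antigen (HBsAg) or detection of HBV DNA in patients with resolved infection". The rise in the first of these must exceed 1 log10.

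**The concern.** Where two operative texts give one patient group different test orders, sites will differ in what they do. A site that works from the flow chart can leave out a safety test that the body of the protocol requires, and it cannot tell from the note which marker triggers DNA.

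Patients of unknown status can be in the trial. Exclusion E 07 begins "Known to be HIV+, HBV+ or hepatitis A, B, or C active Infection", so it acts on what is already known, and the screening laboratory list in Section 12.2 contains no HBV test. Appendix K records that amendment 05 brought in this testing because a risk of hepatitis reactivation had been identified. At stake is a reference DNA value in the patients whose later results would be hardest to interpret without one.

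**Working it through.** No arithmetic applies; the check sets the texts side by side.

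**1. Same patients, same occasion.** Both texts require that the patient is still on treatment at amended protocol 05 and that HBV status was unknown before treatment. Both order the test once, at any time, with clinically indicated repeats. The entry conditions match, so the conflict lies only in the DNA rule.

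**2. The DNA rule.** Within that group, Section 6.5.7 sets no serology condition. Note kk sets one.

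**3. What the trigger could mean.** Taken literally, anti-HBsAg is antibody to the surface antigen, that is, anti-HBs. Taken as a slip, it is HBsAg. The note's own usage does not settle it: it gives HBsAg without a prefix, but it also puts a redundant anti- before two terms that already denote antibodies.

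**4. Consequence under each reading.**

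| HBsAg | anti-HBs | total anti-HBc | DNA under 6.5.7 | DNA under kk, term = HBsAg | DNA under kk, term = anti-HBs |
|---|---|---|---|---|---|
| − | − | + | yes | no | no |
| − | + | + | yes | no | yes |
| + | − | + | yes | yes | no |

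The second and third rows show that the choice of reading matters. The first row does not depend on it: isolated anti-HBc goes without DNA either way.

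**5. Whether the first row needs DNA.** Section 6.5.7 accepts anti-HBc with or without anti-HBs towards resolved infection, and also requires undetectable DNA. Without a DNA result that classification cannot be completed. Of the three reactivation criteria, two rest on an earlier DNA result: a rise needs a prior value, and detection in resolved infection needs the prior classification. Reappearance of HBsAg does not need one.

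**6. Whether another section ranks the two texts.** Section 12.1 directs sites to the flow charts "and described below. The results of the evaluation will be recorded in the e-CRF pages". That links the charts with the procedures in Section 12. It does not say whether a flow-chart note or Section 6.5.7 prevails.

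**The case against.** The strongest reply is that note kk may state the real intent. The flow-chart row is titled as serology, and the amendment 05 table in Appendix K describes the addition as serology without mentioning DNA. Serology with follow-on DNA, loosely summarised in Section 6.5.7, is plausible. This stands as a reason to let the sponsor choose the rule. It does not remove the conflict, because the operative sentence in Section 6.5.7 names viral DNA explicitly.

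It can also be said that note kk points to Section 6.5.7 and that a site performing both tests breaches neither text. That is true of a site that follows the pointer; a site that reads only the note can still omit the test.

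A reader might go further in four ways that the documents do not support:

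- *The pre-treatment baseline is lost.* It is not. Appendix K places amendment 05 after the analysis at the cut-off one year after the last patient entered, so the result is an on-treatment reference.
- *Section 6.5.7 tests everyone on treatment.* It does not; it is limited to patients whose status was unknown before treatment.
- *The table rows measure the size of the problem.* They are marker patterns without prevalence and show only the logic.
- *Routine liver tests cover the gap.* Flow-chart note j schedules chemistry, including AST and ALT, "on D1, D8, D15 and D22 of Cycle 1 and on D1 and D15 of every subsequent cycle". However, Section 12.4.5 does not list routine laboratory tests among the data collected once the final cut-off has passed, so that safeguard should not be assumed for patients treated beyond it.

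**Conclusion.** The inconsistency is real and minor. For the same patients, one current text requires HBV DNA and another makes it depend on an undefined marker. On either meaning of that marker, patients with isolated anti-HBc would go without the on-treatment DNA reference that Section 6.5.7 uses.

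This assumes that some sites work from the note as written. The number affected is not given. It is probably small, since it needs a patient still on treatment, of unknown prior status and with the relevant serology. The documents also do not say whether the one-time tests have already been done. HBsAg testing and clinically indicated repeats remain under both texts, although note kk's DNA condition can be read as applying to the repeat as well.

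Nobody should infer an effect on the efficacy conclusions: ORR, type I error, power and sample size do not depend on this test.

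**What to change.** Reword the test list in note kk to: *HBsAg, anti-HBs, anti-HBc (total and IgM) and HBV DNA in all patients tested*. This matches Section 6.5.7, which then needs no change, and removes the undefined term.

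If the sponsor intends DNA to be conditional, state one defined trigger, HBsAg and/or total anti-HBc positive, in both note kk and Section 6.5.7. That trigger would still capture isolated anti-HBc.

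The first option costs one footnote edit and at most one HBV DNA test per tested patient, which Section 6.5.7 already requires. The second costs an edit in two places and would mean fewer assays than Section 6.5.7 now orders.

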1.2 PK/PD FLOWCHART FOR ISATUXIMAB QW/Q2W + CEMIPILIMAB Q2W

1.2.1 Isatuximab QW/Q2W + cemiplimab Q2W (DL1) - Treatment phase: Cycle 1 (Rich sampling)

Procedure		Treatment Phase									
		C1									
		D1				D4	D8	D15			D22
Cemiplimab	IV infusion	X-----X						X-----X			
	Sample RNT (h)	SOI	EOI	EOI+4h		72h	168h	336h (SOI C1D15)	EOI		
	Sample Time window	[-24h,SOI]	[-5 min,EOI]	±30min		±5h	±24h	[-24h,SOI]	[-5 min,EOI]		
	PK sample ID	S00	S01	S02		S03	S04	S05 ^{c, d}	S06		
	ADA Sample ID ^a	AB00									
Procedure		C1									
		D1				D4	D8	D15			D22
			X-----X				X--		X-----X		X--
Isatuximab	IV infusion		X-----X				X--		X-----X		X--
	Sample RNT (h)	SOI		EOI	EOI+4h	72h	168h (SOI C1D8)	SOI		EOI	SOI
	Sample Time window			±10min	±30min	±5h	[-24h,SOI]			±10min	[-24h,SOI]
	PK sample ID ^b	P00 ^c		P01	P02	P03	P04 ^{c, d}	P05 ^c		P06	P07
	ADA Sample ID ^b	AB00 ^c									

^a For cemiplimab ADA during treatment phase, samples to be collected every third Cycle from C5 (ie, on D1 of C5, C8, C11, C14, etc) till the last study treatment. In response to AEs of special interest, such as anaphylaxis or hypersensitivity, ADA samples closer to the event may be collected, based on the judgment of the Investigator and/or medical monitor. If isatuximab is stopped and cemiplimab treatment continues, cemiplimab ADA samples should be collected as planned per PK/PD flow-chart

^b Isatuximab PK and ADA samples to be collected each cycle till the last study treatment. However, collection can be stopped earlier upon notification from the Sponsor based on the updated knowledge of isatuximab PK and immunogenicity. After FUP 90(±7) days after last IMP administration, no further ADA will be sampled even if the status is positive or inconclusive.

^c Isatuximab predose sample (SOI) may be collected at the same time as the predose sample of cemiplimab (SOI) before cemiplimab infusion start.

^d Sample (ie, cemiplimab 336h drawn at C1D15 and isatuximab 168h drawn at C1D8) must be collected even if the infusion planned for cemiplimab at C1D15 and for isatuximab at C1D8 is not done or delayed.

Abbreviations: AB=Antibody, ADA= Anti-drug antibody, C= Cycle, D= Day, EOI= End of infusion, EOT= End of Treatment (Post-treatment Safety), FUP= Follow-up period (Post-treatment safety), ID= Identifiant, IMP=investigational medicinal product, IV= Intravenous, P=Plasma, PK= Pharmacokinetic, RNT= relative nominal time, S= Serum, SOI= start of infusion,

1.2.2 Isatuximab QW/Q2W + cemiplimab Q2W (DL1) - Treatment phase: Cycle 2 and beyond (Sparse sampling)

Procedure		Treatment Phase											
		C2~C3					C4					C5 and beyond ^d	
		D1		D15			D1		D15			D1	
Cemiplimab	IV infusion	X-----X			X-----X			X-----X			X-----X		X---
	Sample RNT (h)	SOI	EOI		SOI	EOI	SOI	EOI			SOI	EOI	SOI
	Sample Time window	[-24h,SOI]	[-5 min,EOI]		[-24h,SOI]	[-5 min,EOI]	[-24h,SOI]	[-5 min,EOI]			[-24h,SOI]	[-5 min,EOI]	[-24h,SOI]
	PK sample ID	S00	S01		S02	S03	S00	S01			S02	S03	S00
	ADA Sample ID ^a	AB00 (C2)											AB00 ^a
Procedure		C2~C3					C4					C5 and beyond ^d	
		D1		D15			D1		D15			D1	
			X-----X			X---			X-----X			X---	
Isatuximab	IV infusion	SOI		EOI	SOI		SOI		EOI	EOI+1h	SOI		SOI
	Sample RNT (h)			±10min					±10min	±10min			
	Sample Time window												
	PK sample ID ^b	P00 ^c		P01 (C2)	P02 ^c		P00 ^c		P01	P02	P03 ^c		P00 ^c
	ADA Sample ID ^b	AB00 ^c					AB00 ^c						AB00 ^c

- ^a For cemiplimab ADA during treatment phase, samples to be collected every third Cycle from C5 (ie, on D1 of C5, C8, C11, C14, etc) till the last study treatment. In response to AEs of special interest, such as anaphylaxis or hypersensitivity, ADA samples closer to the event may be collected, based on the judgment of the Investigator and/or medical monitor. If isatuximab is stopped and cemiplimab treatment continues, cemiplimab ADA samples should be collected as planned per PK/PD flow-chart
- ^b Isatuximab PK and ADA samples to be collected each cycle till the last study treatment. However, collection can be stopped earlier based on the updated knowledge of isatuximab PK and immunogenicity. After FUP 90(±7) days after last IMP administration, no further ADA will be sampled even if the status is positive or inconclusive.
- ^c Isatuximab predose sample (SOI) may be collected at the same time as the predose sample of cemiplimab (SOI) before cemiplimab infusion start
- ^d Follow-up procedures after the extended safety period of 90 days after last study treatment dose will not be performed anymore for patients still under treatment at the time of amended protocol 05.

Abbreviations: AB=Antibody, ADA= Anti-drug antibody, C= Cycle, D= Day, EOI= End of infusion, EOT= End of Treatment (Post-treatment Safety), FUP= Follow-up period (Post-treatment safety), ID= Identifiant, IMP=investigational medicinal product, IV= Intravenous, P=Plasma, PK= Pharmacokinetic, RNT= relative nominal time, S= Serum, SOI= start of infusion

1.2.3 Isatuximab QW/Q2W + cemiplimab Q2W (DL1) - End of treatment and follow-up periods

Procedure		EOT	FUP	
Cemiplimab	Sample RNT (h)	30 (±7) days after last IMP admin	60 (±7) days after last IMP admin	90 (±7) days after last IMP admin
	PK sample ID	SF00	SF01	
	ADA Sample ID	ABF00		ABF01
Procedure		EOT	FUP	
Isatuximab	Sample RNT (h)	30 (±7) days after last IMP admin	60 (±7) days after last IMP admin	90 (±7) days after last IMP admin
	PK sample ID	PF00		
	ADA Sample ID	ABF00		ABF01

NOTE: Follow-up procedures after the extended safety period of 90 days after last study treatment dose will not be performed anymore for patients still under treatment at the time of amended protocol 05. ADA and PK collection was interrupted at cut-off of primary analysis planned 6 months after LPI.

Abbreviations: AB=Antibody, ADA= Anti-drug antibody, C= Cycle, D= Day, EOI= End of infusion, EOT= End of Treatment (Post-treatment Safety), FUP= Follow-up period (Post-treatment safety), ID= Identifiant, IMP=investigational medicinal product, IV= Intravenous, LPI=last patient in, P=Plasma, PK= Pharmacokinetic, RNT= relative nominal time, S= Serum, SOI= start of infusion

1.3 PK/PD FLOWCHART FOR ISATUXIMAB QW/Q2W + CEMIPILIMAB Q4W

1.3.1 Isatuximab QW/Q2W + cemiplimab Q4W (DL-1) - Treatment phase: Cycle 1 (Rich sampling) and Cycle 2

Procedure		Treatment Phase												
		C1							C2					
		D1			D4	D8	D15		D22	D1		D15		
Cemiplimab	IV infusion	X-----X									X----X			
	Sample RNT (h)	SOI	EOI	EOI+4h	72h	168h	336h				SOI (672h at C1D29)	EOI	336h	
	Sample Time window	[-24h,SOI]	[-5 min,EOI]	±30min	±5h	±24h					[-24h,SOI]	[-5 min,EOI]		
	PK sample ID	S00	S01	S02	S03	S04	S05 ^e				S00 ^d	S01	S02 ^e	
	ADA Sample ID ^a	AB00									AB00			
Procedure		C1							C2					
		D1			D4	D8	D15		D22	D1		D15		
			X-----X			X	X-----X		X		X----X		X	
Isatuximab	IV infusion		X-----X				X	X-----X		X		X----X		
	Sample RNT (h)	SOI		EOI	EOI+4h	72h	168h (SOI D8)	SOI	EOI	SOI	SOI		EOI	SOI
	Sample Time window		-	±10min	±30min	±5h	[-24h,SOI]	[-24h,SOI]	±10min	[-24h,SOI]		-	±10min	[-24h,SOI]
	PK sample ID ^b	P00 ^c		P01	P02	P03	P04 ^d	P05	P06	P07	P00 ^c		P01	P02
	ADA Sample ID ^b	AB00 ^c									AB00 ^c			

- a For cemiplimab ADA during treatment phase, samples to be collected every third Cycle from C5 (ie, on D1 of C5, C8, C11, C14, etc) till the last study treatment. In response to AEs of special interest, such as anaphylaxis or hypersensitivity, ADA samples closer to the event may be collected, based on the judgment of the Investigator and/or medical monitor. If isatuximab is stopped and cemiplimab treatment continues, cemiplimab ADA samples should be collected as planned per PK/PD flow-chart
- b Isatuximab PK and ADA samples to be collected each cycle till the last study treatment. However, collection can be stopped earlier upon notification from the sponsor based on the updated knowledge of isatuximab PK and immunogenicity. After FUP 90(±7) days after last IMP administration, no further ADA will be sampled even if the status is positive or inconclusive.
- c Isatuximab predose sample (SOI) may be collected at the same time as the predose sample of cemiplimab (SOI) before cemiplimab infusion start.
- d Sample (ie, T672h at C1D29 corresponding to C2D1 for cemiplimab and C1D8 T168h for isatuximab) must be collected even if the infusion planned for cemiplimab at C2D1 and/or infusion planned for isatuximab at C1D8 is not done or delayed.
- e Cemiplimab predose sample on D15 may be collected on at the same time as the predose sample of isatuximab (SOI) before isatuximab infusion start
- Abbreviations: AB=Antibody, ADA= Anti-drug antibody, C= Cycle, D= Day, EOI= End of infusion, EOT= End of Treatment (Post-treatment Safety), FUP= Follow-up period (Post-treatment safety), ID= Identifiant, IMP=investigational medicinal product, IV= Intravenous, P=Plasma, PK= Pharmacokinetic, RNT= relative nominal time, S= Serum, SOI= start of infusion,

1.3.2 Isatuximab QW/Q2W + cemiplimab Q4W (DL-1) - Treatment phase: Cycle 3 and beyond (Sparse sampling)

Procedure		Treatment Phase							
		C3			C4				C5 and beyond ^e
		D1		D15	D1			D15	D1
Cemiplimab	IV infusion	X-----X			X-----X				X
	Sample RNT (h)	SOI	EOI	336h	SOI	EOI		336h	SOI
	Sample Time window	[-24h,SOI]	[-5 min, EOI]		[-24h,SOI]	[-5 min, EOI]			[-24h,SOI]
	PK sample ID	S00	S01	S02 ^c	S00	S01		S02 ^{c, d}	S00
	ADA Sample ID ^a								AB00 ^a
Procedure		C3			C4				C5 and beyond ^e
		D1		D15	D1			D15	D1
Isatuximab	IV infusion		X	X	X----X			X	X
	Sample RNT (h)	SOI		SOI	SOI	EOI	EOI+1h	SOI	SOI
	Sample Time window			[-24h,SOI]		±10min	±10min	[-24h,SOI]	
	PK sample ID ^b	P00 ^c		P02	P00 ^c	P01	P02	P03 ^d	P00 ^c
	ADA Sample ID ^b	AB00 ^c			AB00 ^c				AB00 ^c

- a For cemiplimab ADA during treatment phase, samples to be collected every third Cycle from C5 (ie, on D1 of C5, C8, C11, C14, etc) till the last study treatment. In response to AEs of special interest, such as anaphylaxis or hypersensitivity, ADA samples closer to the event may be collected, based on the judgment of the Investigator and/or medical monitor. If isatuximab is stopped and cemiplimab treatment continues, cemiplimab ADA samples should be collected as planned per PK/PD flow-chart
- b Isatuximab PK and ADA samples to be collected each cycle till the last study treatment. However, collection can be stopped earlier upon notification from the sponsor based on the updated knowledge of isatuximab PK and immunogenicity. After FUP 90(±7) days after last IMP administration, no further ADA will be sampled even if the status is positive or inconclusive.
- c Isatuximab predose sample (SOI) may be collected at the same time as the predose sample of cemiplimab (SOI) before cemiplimab infusion start.
- d Cemiplimab predose sample on C4D15 may be collected on at the same time as the predose sample of isatuximab (SOI) before isatuximab infusion start.
- e Follow-up procedures after the extended safety period of 90 days after last study treatment dose will not be performed anymore for patients still under treatment at the time of amended protocol 05.

Abbreviations: AB=Antibody, ADA= Anti-drug antibody, C= Cycle, D= Day, EOI= End of infusion, EOT= End of Treatment (Post-treatment Safety), FUP= Follow-up period (Post-treatment safety), ID= Identifiant, IMP=investigational medicinal product, IV= Intravenous, P=Plasma, PK= Pharmacokinetic, RNT= relative nominal time, S= Serum, SOI= start of infusion

1.3.3 Isatuximab QW/Q2W + cemiplimab Q4W (DL-1) - End of treatment and follow-up periods

Procedure		EOT	FUP	
Cemiplimab	Sample RNT (h)	30 (±7) days after last IMP admin	60 (±7) days after last IMP admin	90 (±7) days after last IMP admin
	PK sample ID	SF00	SF01	
	ADA Sample ID	ABF00		ABF01
Procedure		EOT	FUP	
Isatuximab	Sample RNT (h)	30 (±7) days after last IMP admin	60 (±7) days after last IMP admin	90 (±7) days after last IMP admin
	PK sample ID	PF00		
	ADA Sample ID	ABF00		ABF01

NOTE: Follow-up procedures after the extended safety period of 90 days after last study treatment dose will not be performed anymore for patients still under treatment at the time of amended protocol 05. ADA and PK collection was interrupted before amended protocol 05.

Abbreviations: AB=Antibody, ADA= Anti-drug antibody, C= Cycle, D= Day, EOI= End of infusion, EOT= End of Treatment (Post-treatment Safety), FUP= Follow-up period (Post-treatment safety), ID= Identifiant, IMP=investigational medicinal product, IV= Intravenous, P=Plasma, PK= Pharmacokinetic, RNT= relative nominal time, S= Serum, SOI= start of infusion

